### Statistical Methods

*Design:* Caregivers will be randomized into two groups: Experimental In-Home Technology System and Limited In-Home Technology System. Subjects will be randomized 1:1. Randomization of participants in each group will be determined by members (i.e., graduate students listed in this protocol) of the research team and staff members completing the installation will not be aware of which group the caregivers are assigned to. With a total N of 80 caregivers in two conditions and measures repeated four times, a comparison between groups using ANOVA will have .80 power to detect a medium effect size at  $p=.05$ .

*Analysis:* Descriptive statistics will be used to summarize all the clinical characteristics and demographic outcomes. These will be summarized overall, by treatment group, by assessment time, and by treatment group and time. Continuous variables will be summarized using means, standard deviations, and ranges. Categorical data will be summarized by number and percent. To evaluate the treatment effects, we will use repeated measures ANCOVAs. The respective baseline measure of each outcome variable will be included as a covariate in the appropriate analysis (e.g., baseline depression scores from the baseline measurement of the CES-D, will be used as a covariate in examining treatment effects of depression). The other predictors will be treatment group, and time (baseline, 6-months, and 9- months for caregiver outcomes). To

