evaluate treatment effects, an interaction term between treatment group and time will be included to examine treatment group-related differences controlling for baseline to later assessments for each outcome. Each significant interaction will be followed up with paired t-tests to examine treatment differences at each set of time points. Although this study involves 4 outcomes, we do not plan formal multiple comparison adjustments if the results fit a coherent pattern that is consistent with the context of similar studies. In this case, each result will reinforce the other, rather than detracting from one another, as required by formal multiple comparisons adjustments such as Bonferroni. Conversely, if only one or a very few measures reach statistical significance and their directions and/or magnitudes do not coherently fit with our prior expectations, then we will note that the result(s) with  $p < 0.05$  lack plausibility and could be due to chance, despite meeting the conventional cutoff for statistical significance.

*Missing Data:* If subjects either cannot or refuse to complete surveys we will use a sensitivity analysis approach in dealing with these missing data by performing analysis with 2 versions of scores: 1) with missing item interpolated using mean replacement by group, and 2) only using responses with 0% missing data. If the results differ for the two approaches, then we will report on the differences.

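### The only planned time-point treatment comparisons depend on a significant interaction, and no baseline-adjusted arm difference with a 95% CI is planned for each of the four scales

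*SAP*

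**What the plan says.** All references are to the SAP, Statistical Methods.

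- **Model.** "To evaluate the treatment effects, we will use repeated measures ANCOVAs". The baseline value of each outcome is a covariate. For the rest: "The other predictors will be treatment group, and time (baseline, 6-months, and 9- months for caregiver outcomes". Baseline is therefore listed both as a covariate and as a level of time, and month 3 is not listed.
- **Term that carries the treatment effect.** "an interaction term between treatment group and time will be included to examine treatment group-related differences controlling for baseline to later assessments for each outcome".
- **Follow-up.** "Each significant interaction will be followed up with paired t-tests to examine treatment differences at each set of time points".
- **Descriptive tables.** "These will be summarized overall, by treatment group, by assessment time, and by treatment group and time". Their content: "Continuous variables will be summarized using means, standard deviations, and ranges". No condition is attached. They are introduced as covering clinical characteristics and demographic outcomes, so their coverage of the four scales is inferred.
- **Reading four outcomes.** "Although this study involves 4 outcomes, we do not plan formal multiple comparison adjustments if the results fit a coherent pattern". The fallback applies "if only one or a very few measures reach statistical significance and their directions and/or magnitudes do not coherently fit with our prior expectations"; such results are then to be described as possibly due to chance.

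Neither the Primary Outcomes section nor Statistical Methods names an adjusted between-arm difference or a confidence interval for any scale.

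**The concern.** Making a comparison conditional on p < .05 is a significance filter on estimation. Where passing goes with a large observed difference, estimates seen after the filter are biased away from zero. A scale that fails the filter has no planned interval, so a reader cannot tell a benefit that was excluded from one that 80 caregivers could not measure.

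This matters more here because the plan replaces formal multiplicity adjustment with a judgement of whether the direction and size of the results fit expectations. That judgement needs comparable estimates, with their precision, for all four scales. If it rests on filtered estimates, it compares selected values with nothing.

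The choice of the paired t-test is a separate matter. A correct between-arm test placed after the same condition would be filtered in the same way.

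**Working it through.** **1. The plan's own figure.** The SAP states .80 power for a between-group ANOVA with N = 80, two arms, four measures, a medium effect and p = .05. Assume medium means f = .25 and the correlation between measures is ρ = .5; neither is in the documents. Then λ = N·f²·m / [1 + (m − 1)ρ] = 80 × .0625 × 4 / 2.5 = 8.0. With 1 and 78 df the power is .798, so the figure reproduces. It is the power of the between-group comparison, not of the interaction on which follow-up depends.

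**2. Inputs for the filter.** From the SAP: 80 caregivers randomized 1:1, hence n = 40 per arm; interaction tested at .05; time levels baseline, 6 and 9 months. Assumed: complete data, compound symmetry with ρ = .5 or .7, and a true difference of d SD at both 6 and 9 months and none at baseline. The simulated filter is the ordinary group-by-time F with 2 and 156 df. The estimate is the baseline-adjusted 9-month arm difference, the quantity a repaired follow-up would report.

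**3. How often the filter is passed.** The true arm differences are (0, d, d), with mean 2d/3. The squared deviations sum to (4/9 + 1/9 + 1/9)d² = (2/3)d². So λ = (n/2)(2/3)d²/(1 − ρ) = 13.33·d²/(1 − ρ). At ρ = .5:

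- d = .2: λ = 1.07, pass rate about 14%
- d = .3: λ = 2.40, about 26%
- d = .5: λ = 6.67, about 62 to 63%

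At ρ = .7 the rates are about 20%, 41% and 85%. With a true .3 SD on all four scales and ρ = .5, about 4 × .26 ≈ 1 scale would be followed up.

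**4. What the passing estimates look like.** Simulated trials, 4,000 to 20,000 per setting; separate runs agree to about .02 SD.

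| True difference (SD) | Mean over all trials | Mean after filter, ρ = .5 | Mean after filter, ρ = .7 |
|---|---|---|---|
| .2 | .20 | about .36 (1.8 times) | about .35 |
| .3 | .30 | about .45 (1.5 times) | about .40 |
| .5 | .50 | about .57 (1.14 times) | about .53 (1.06 times) |
| .8 | .80 | about .81 | about .80 |

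Reported for every scale, the estimate averages the truth, so the filter causes the inflation.

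**5. No true effect, ρ = .5.** The adjusted difference has standard error √[2(1 − ρ²)/n] = √(2 × .75/40) = .194. Its mean absolute value is about .194 × .798 = .155, or about .16 in simulation. Among the 5% of null scales that pass, it is about .31. A null scale that passes therefore looks much like a passing scale with a true .2 SD (about .36).

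**6. Adding the baseline covariate.** With baseline also a covariate and the three time levels kept, the pass rate at ρ = .5 rises to 30% for d = .3 and 74% for d = .5. The selected means stay similar (.47 and .57).

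**7. Baseline only as a covariate.** The interaction then compares the arm difference at 6 months with that at 9 months. For a constant effect this is d − d = 0. The filter is passed in about 5% of trials whatever d is, and the mean after it is about the truth (.31 for .3, .50 for .5). There is no inflation, but about 95% of trials with a real, constant effect get no follow-up.

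**The case against.** The strongest reply is that the SAP conditions a test and does not restrict reporting. Following up an omnibus test only when it is significant is a common convention. The ANCOVA, with its group and interaction terms, is fitted for each outcome whatever the p-value. Means and SDs by arm and visit are planned without condition, and a crude difference can be read from them. The multiplicity paragraph implies that all four results are seen together.

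Much of this stands. A reader might infer that every treatment difference the plan yields is selected, or that scales missing p < .05 get no estimate at all. The documents do not support either reading. What the reply does not supply is an adjusted difference at a visit with its interval. The descriptive tables are unadjusted and have no interval. The SAP does not say that the group term will be reported, and with the listed time levels that term averages over baseline.

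Three further limits also stand. The inflation factors describe a corrected between-arm estimate placed after the filter, not the paired t-tests the plan names. The SAP does not say where the sizes used in the plausibility judgement come from, so their being filtered values is an inference. It would also go too far to say that size can never separate chance from benefit: after the filter at ρ = .5, about .31 under no effect is clearly below about .57 at a true .5 SD.

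**Conclusion.** The point holds in a limited form. The only prespecified comparisons by time point are conditional on a significant interaction, and no baseline-adjusted arm difference with a 95% CI is planned for each scale.

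The consequence depends on a model detail. With baseline as a time level, as the SAP lists it, the filter inflates small effects (about 1.8 times at .2 SD, 1.5 times at .3 SD), inflates .5 SD only modestly (1.06 to 1.14 times) and is negligible at .8 SD. With baseline as a covariate only, it does not inflate but usually suppresses follow-up of a constant effect. A reader might infer that inflation is certain; it is not. These figures rest on 40 per arm, complete data, compound symmetry with correlation .5 or .7, and an effect constant from month 6. Under either model reading, the unconditional estimate is the better choice. The change should be made, but it does not undermine the trial's design.

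**What to change.** Remove the condition on a significant interaction. For each of the four scales, whatever the interaction p-value, report the baseline-adjusted experimental-minus-control difference with its 95% CI at each post-baseline visit in the model. State that the judgement on direction and size applies to all four estimates and their intervals, not only to those with p < .05.

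The cost is SAP wording and one table from the model already planned. No new data are needed.

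### The missing-data rule names no primary analysis, leaves its replacement mean and units undefined, and relies on single group-mean filling that makes standard errors too small

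*SAP*

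**What the plan says.** The SAP, Statistical Methods, states "To evaluate the treatment effects, we will use repeated measures ANCOVAs". The baseline score of each outcome is a covariate. The other predictors are given as "treatment group, and time (baseline, 6-months, and 9- months for caregiver outcomes", and the treatment effect is judged through the interaction: "an interaction term between treatment group and time will be included". The 3-month questionnaire is collected but is not in that list of times.

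The Missing Data paragraph of the same section opens: "If subjects either cannot or refuse to complete surveys we will use a sensitivity analysis approach in dealing with these missing data". The two sets of scores are "1) with missing item interpolated using mean replacement by group, and 2) only using responses with 0% missing data". The only rule for disagreement is "If the results differ for the two approaches, then we will report on the differences".

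No missing rate is given, no limit is set on how much may be filled, and neither analysis is called primary. The Protocol text adds nothing on this.

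For 80 caregivers, each measured four times, the Design paragraph gives the planned power: "a comparison between groups using ANOVA will have .80 power to detect a medium effect size".

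**The concern.** A repeated measures ANCOVA needs a score at every analysed visit, so the missing-data rule decides who is analysed and with what error. Three choices that govern the result are open:

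- **The mean.** Replacement by group could use the mean at that visit or a mean over all visits.
- **The extent of filling.** The clause speaks of an item, but what triggers it is a caregiver who does not complete the survey. If every item of an unreturned form is filled with its group-by-visit item mean, the total is simply the group-by-visit mean score.
- **The unit of 0% missing.** It could be a form, a visit or a caregiver.

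A filled group mean adds nothing to the within-group spread, yet it is counted in the sample size and the error degrees of freedom. Standard errors are then too small and false positives too frequent. Both analyses are presented as sensitivity analyses, but there is no main analysis for them to test. If one reaches p < .05 and the other does not, the plan has no answer. The SAP also plans no formal adjustment over its four outcomes when their results look coherent, so nothing elsewhere absorbs a raised per-test error rate.

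**Working it through.** **Inputs.** From the SAP: 80 caregivers randomized 1:1 (40 per arm), four measures, significance level .05, power .80, group x time test with baseline covariate. Assumed, because the documents are silent: medium effect f = .25; correlation between visits .5 (also .7); missing rates 5, 10 and 20%; loss completely at random; baseline complete; no treatment effect when type I error is assessed.

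**The plan's own figure.** For the between-group test with m measures, noncentrality = f² × N × m / (1 + (m − 1) × correlation) = .0625 × 80 × 4 / 2.5 = 8.0. With F(1, 78) the power is .798, so the stated .80 reproduces. Correlations of .3 and .7 give .893 and .708, so .5 is inferred, not stated.

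**Why mean filling shrinks the error.** Take one visit with n = 40 per arm and o observed. The sum of squares comes from o values but is divided by n − 1, and the SE uses n instead of o. Reported SE / correct SE = sqrt[((o − 1)/(n − 1)) × (o/n)], and type I error is 2 × P(Z > 1.96 × ratio).

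| Missing | o | SE ratio | Type I error |
|---|---|---|---|
| 5% | 38 | .949 | .063 |
| 10% | 36 | .899 | .078 |
| 20% | 32 | .797 | .118 |

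**Group x time test, group-by-visit mean.** Simulated repeated measures ANCOVA with Greenhouse-Geisser correction, 4,000 runs per cell (Monte Carlo SE near 13%: sqrt(.13 × .87 / 4000) = .005). Loss was either at the stated rate at every visit or building up to it by month 9.

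| Visits as time levels | 5% missing | 10% missing | 20% missing |
|---|---|---|---|
| 3, 6, 9 months | 5.5-6.7% | 6.9-9.5% | 10-15% |
| 6, 9 months | 5.7-6.3% | 6.4-7.9% | 9.6-12% |
| baseline, 6, 9 months (as listed in the SAP) | 5.9-7.1% | 7.7-8.6% | 12-15% |

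A separate simulation with 10,000 runs per setting gave 10-15% when every visit lost 20% and 9.2-12.0% when loss reached 20% only at month 9. The same tests on full data gave 4.6-6.5%. Overall, at 20% missing the range is about 9-15%.

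**Items or whole scores.** Filling single items by group-by-visit item mean (12-item scale) gave 4.3, 5.5 and 6.6% at 1, 2 and 5% of items missing. At 20% of items it gave about 12.5-14%. At the same 5% rate, whole-score filling on 3, 6 and 9 months gave 5.5-6.7%. The missing rate drives the inflation, not the level at which values are filled.

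**Mean pooled over visits, 20% missing.** On follow-up visits group x time is 4-5%, but the group main effect is 9-13%. If baseline is also a time level and enters the pooled mean, the figures are 6-8% and 8-11%.

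**Complete responses only.** Type I error for group x time stays at 4-6% under random loss. If any missed visit removes the caregiver, the number kept depends on the pattern of loss. Power uses the formula above with N − 2 error degrees of freedom.

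| Missing | Pattern | Caregivers kept | Power |
|---|---|---|---|
| 20% | visits missed independently, 3 visits | 80 × .8³ = 41 | .51 |
| 20% | visits missed independently, 2 visits | 80 × .8² = 51 | .60 |
| 20% | dropout building to 20% | 80 × .8 = 64 | .70 |
| 10% | visits missed independently, 3 visits | 80 × .9³ = 58 | .66 |
| 10% | visits missed independently, 2 visits | 80 × .9² = 65 | .71 |
| 10% | dropout building to 10% | 80 × .9 = 72 | .75 |

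**The case against.** The strongest defence is that both analyses are always run and any difference must be reported. This stands in part. In null simulations at 10-20% missing, both analyses were significant together in only about 3-5% of runs, so a false positive that leaves no visible conflict is not more frequent than the nominal rate. But visibility does not settle which result carries the conclusion.

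A second defence is that the clause concerns stray skipped items, where the effect is negligible. That is true at 1-2% of items. But the paragraph is triggered by uncompleted surveys and sets no limit. If it covers items only, the plan's only way to deal with a missed questionnaire is to leave it out.

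Three stronger readings are tempting, and the documents do not support them:

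- **That the plan has a 10-15% false-positive rate.** This needs a 20% missing rate that the documents never give and a per-visit mean that they do not specify. With a mean pooled over follow-up visits, group x time is not inflated at all.
- **That harm arises only if whole scores are filled.** At equal missing rates, item filling and whole-score filling behave alike.
- **That the complete-response analysis keeps only about half the sample.** The figure of 41 of 80 needs visits to be missed independently and whole caregivers to be dropped. The SAP does not define the unit, and dropout building to 20% keeps 64.

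**Conclusion.** The concern holds as a defect of specification and method. No primary analysis is named; the type of mean, the extent of filling and the unit of 0% missing are undefined; and single group-mean replacement understates standard errors however those gaps are filled. Which test suffers depends on the mean chosen: mainly group x time and also the group effect with per-visit means, mainly the group effect with pooled means.

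The size is conditional on the missing rate: slight at 5%, material at 20%. All figures assume loss completely at random. Loss related to burden or mood was not examined. The complete-response analysis protects the error rate under random loss at a cost in power that ranges from modest (.75) to severe (.51), so it is not an attractive primary analysis either. This should be fixed before the data are analysed. Confidence is high on the wording and medium on the size.

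**What to change.** - Drop group-mean replacement.
- Name one primary analysis: a likelihood-based repeated-measures mixed model with baseline score as covariate, group, visit and group x visit. It should use all observed follow-up visits (state which), no filled scores, and a small-sample degrees-of-freedom correction.
- Prorate a partly answered scale from the caregiver's own answered items when a pre-stated share is present, for example at least half.
- Keep the 0%-missing analysis as a labelled sensitivity analysis and define its unit.

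**Cost.** SAP wording and a change of fitting procedure in standard software; no new data. Confidence intervals will be wider, and correctly so, by up to about 25% at an assumed 20% missing (1/.797 = 1.25).

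**Check of the fix.** With 20% missing independently at each visit and correlation .5, an unstructured mixed model gave group x visit type I error of .061 (three follow-ups, 962 runs) and .058 (two, 2,757 runs), against .144 and .122 for mean filling in the same runs. Power for the average group effect was about .74, against .79-.81 with no missing data and .49-.60 with complete responses only. This check has limits: it used simple residual degrees of freedom, not the recommended correction; its power figures are for the average group effect, not the interaction; and the gap to complete responses would be smaller under dropout.
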